5.1.3 Packaging and Labeling

The Sponsor will supply all study drugs for this trial. The Investigational Site personnel and the subjects will be blinded to the treatment.

The study drugs will be supplied in 15-count high-density polyethylene bottles with child resistant closures.

The double-blind labeling kit (carton) will contain one 15-count bottle of OE Norvasc[®] tablet or matched placebo for the OE Norvasc[®] tablet and one 15-count bottle of OE Celebrex[®] capsule or matched placebo for the Celebrex[®] capsule.

Medications will be labeled according to the requirements of local law and legislation. Each patient kit, and the two bottles of study drug within the kit, will be labeled with a randomization number. Label text will be approved according to agreed Kitov procedures, and a copy of the labels will be made available to the study site upon request. Copies of the labels will be available in the study files.

Copies of the product labeling for the two commercial formulations (amlodipine tablets and celecoxib capsules) are included in Appendices F and G, respectively.

5.1.4 Storage and Handling

At the Investigational Site, all study drugs will be stored in a locked, secure area to prevent unauthorized access. The study drugs should be stored in compliance with the label requirements. The study drugs will be stored in the original packaging at controlled room temperature (15-30°C or 59-86°F) protected from light. The subjects will be instructed to store the study drug provided in the take home kits in the original packaging at controlled room temperature protected from light.

5.2 Randomization

This is a randomized, double blind, placebo controlled study. Subjects will be randomized 3:3:1 to one of three treatment arms:

1. OE Norvasc[®] tablet (10 mg amlodipine besylate) + OE Celebrex[®] capsule (200 mg celecoxib);
2. OE Norvasc[®] tablet (10 mg amlodipine besylate) + matched placebo for OE Celebrex[®] capsule;
3. Matched placebo for OE Norvasc[®] tablet + matched placebo for OE Celebrex[®] capsule.

Randomization will take place on Day 0 when the subject returns to clinic and is found to have hypertension based upon the ABPM recordings and continues to meet eligibility criteria following baseline procedures.

A computer-generated randomization schedule will be used for assigning the sequence in which subjects are assigned to treatment arms. The randomization code will be prepared in blocks of 7. Initial shipments to individual Investigational sites will include 5 patient kits with sequential randomization numbers. As subjects are enrolled, the Investigator will take the next sequential kit number in the block provided and assign it to the subject. The Investigational sites will be re-supplied in the same fashion (i.e., 5 patient kits).

Approximately 105 subjects are to be randomized. Therefore, a sufficient number of subjects will be screened so as to achieve approximately 105 subjects entering the randomization phase (starting at Day 0). Once the 105th subject is randomized to treatment (Day 0), any subject that is currently participating in the washout period will be allowed to complete the washout period and if found eligible will be enrolled into the trial. These subjects will continue to be randomized 3:3:1 as noted above. No further subjects will be brought in for the Initial Screening Visit once the 105th subject is randomized.

In the event of a medical emergency or a serious TEAE that is unexpected (as defined in Section 8.1.4) and possibly related to the study drug(s) (i.e., an adverse reaction or suspected adverse reaction as defined in Section 8.1.3), the blind will be broken for the subject that experiences the event. An emergency code break envelope for each subject will be provided to each Investigational Site and also to the Pharmacovigilance Officer at PM Clinical LTD. In the event that the Investigational Site personnel need to unblind the study treatment and cannot access the relevant code break envelope at the site, they can contact the Pharmacovigilance Officer at any time at:

5.3 Study Drug Administration

All subjects will take study drugs by mouth qd for 14 days (Days 0-13) for a total of 14 doses. With the exception of Days 6 and 13, when study drug intake is at the time of fitting the ABPM and of Day 7, when study drug intake is 24 hours \pm 1 hour later, the subjects shall be instructed to take the study drugs between 0700 and 1000 hours, and preferably at approximately the same time each day. At each dose, subjects will take one capsule from each of the two containers (i.e., an OE Norvasc[®] tablet or matched placebo for the OE Norvasc[®] tablet and an OE Celebrex[®] capsule or matched placebo for the OE Celebrex[®] capsule).

The first dose of study drugs (morning dose on Day 0) will be taken in the clinic. Study Day 6 and Study Day 13 doses will also be taken in clinic. All remaining doses will be self-administered at home. Subjects will be provided with a diary to record the details of study drug administration including the time each dose is taken.

Study drugs will only be dispensed to subjects randomized to treatment under this protocol, and only as directed by this protocol. Administration of study drugs will be accurately recorded in each subject's source documents and CRF.

5.4 Measuring Subject Compliance

A total of 14 doses of study drugs will be administered. The first dose will be administered in the clinic on Study Day 0, as will Study Day 6 and Day 13 doses. The remainder of the doses will be self-administered at home. Subjects will be provided with a diary to record details of study drug administration for each dose (date, time, number of capsules), and will be instructed to return the completed diary at the Day 6, Day 7, and Day 13 clinic visits.

Subjects will also be instructed to bring both of their study drug containers back to the clinic at Day 6, Day 7, and Day 13. The Investigational Site personnel will collect the study drug containers, and will count and record unused study drug.

5.5 Drug Accountability

In accordance with current GCP, the Investigational Site will account for all study drug supplies. Details of receipt, storage, administration, and return or destruction will be recorded in the study drug accountability record according to the standard operating procedure of the Investigational Site. Copies of the study drug accountability record will be provided to the Sponsor.

Investigational supplies will be retained at the clinical site pending instructions for disposition by the Sponsor at the end of the study.

5.6 Concomitant Medications

All medications (or treatments) other than study drugs taken or received by the subject at any time during the study from the first dose of study drugs through the final study visit assessment will be considered concomitant medications. Use of all concomitant medications, including any change in therapy, must be recorded and updated in the source documentation and on the CRF.

Subjects are not to consume any NSAIDs (other than study drug) from the initial screening visit to the final study visit (Day 28). Subjects will be instructed to take acetaminophen for any pain that develops from the time of enrollment until completion of the study or for the treatment of any fever that occurs and is deemed to require pharmacological therapy during the course of this study.

Subjects are not to consume any calcium channel blocker (other than study drug) from the initial screening visit to Day 14. Further, a subject will not be eligible to participate in this trial if they have ever taken calcium channel blockers for any indication.

Subjects are not to consume their current BP medication from the initial screening visit to Day 14. Following the Day 14 evaluations, subjects will be instructed to resume taking their prescribed BP medication as directed by the study doctor or general practitioner. If subjects are found to be too hypertensive to continue safely in the study after 7 days of study drug administration, they will be removed from the study and instructed to resume taking their prescribed BP medication as directed by the study doctor or general practitioner.

Subjects are not to take any other investigational drugs beginning 30 days prior to the first dose of study drugs and continuing until the final study visit (Day 28).

Information about the known drug interactions with amlodipine and celecoxib can be found in the product labelings for prescription amlodipine tablets and celecoxib capsules which are included in Appendices F and G, respectively.

Subjects are to avoid consumption of grapefruit juice for the duration of the study.

6. SCHEDULE OF EVENTS

The schedule of events is provided in tabular format in Appendix A, and is summarized below by study visit.

6.1 Screening Visits

6.1.1 Initial Screening Visit (Day -14 to -10)

The Investigator is responsible for keeping a record of all subjects screened for entry into the study and subsequently excluded. The reason(s) for exclusion will be recorded in the source documents.

Each subject will be provided with oral and written information (ICF) describing the study and will have any questions answered. Written informed consent must be obtained prior to performing any screening evaluations.

The initial screening visit will occur on Day -14 to -10. Subjects will undergo the following screening procedures:

1. Record demographic data (date of birth/age at Screening, gender, and race);
2. Complete medical history, including baseline concurrent illness assessment;
3. Review and record medications taken within 30 days prior to initial screening visit;
4. Height, body weight while only wearing underwear and a light gown, and BMI as determined by $\text{Weight (kg)/Height (m)}^2$;
5. Comprehensive physical examination (see Section 8.2);
6. Vital signs (BP, pulse rate, respiration rate, and oral body temperature);
7. 12-lead ECG;
8. Blood sampling for hematology and serum chemistry (see Appendix B for list of tests);
9. Serum pregnancy test for WCBP only;
10. Collection of urine for urinalysis (see Appendix B for list of tests);
11. Urine drug screen (see Appendix B for list of tests);
12. Assessment of inclusion and exclusion criteria.

Subjects who meet eligibility criteria based on the above initial screening assessments will be instructed as follows:

1. Cease taking current BP medication;

2. Do not take any NSAIDs (other than the study drug) for the duration of the study (through Day 28);
3. Use acetaminophen for the treatment of any pain or fever that develops while on study and that is deemed to require pharmacological therapy;
4. Do not take any calcium channel blocker (other than study drug) through the Day 14 evaluations;
5. Do not take any other investigational drugs for the duration of the study (through Day 28);
6. For WCBP: Use adequate contraceptive methods for the duration of the study (through Day 28). For this study, a woman who has been surgically sterilized or who has been in a state of amenorrhea for more than two years will be deemed not to be of child bearing potential;
7. Return to the clinic in 9 to 13 days (on the morning of Day -1);
8. Do not consume any grapefruit juice for the remainder of the study.

Monitoring for PTAEs will begin upon completion of the initial screening visit procedures and will continue through the 9 to 13 days of washout, the final screening visit on Day -1, and the baseline procedures on Day 0 (i.e., prior to the administration of the first dose of study drugs). Any untoward medical occurrence that initiates or worsens after completion of the initial screening visit procedures and before administration of the first dose of study drugs will be recorded as a PTAE.

6.1.2 Final Screening Visit (Day -1)

Subjects will return to clinic after 9 to 13 days of washout for their final screening visit (Day -1). They will undergo the following procedures:

1. Solicit history of PTAEs since prior visit;
2. Review and record medications taken since prior visit.

Those subjects who continue to meet eligibility criteria will be given an ABPM, instructed in its use, and have the positioning of their ABPM checked. They will be instructed to wear it at all times for the next 25 hours and to return to the clinic the following day (Day 0).

6.2 Study Day 0

Subjects will return to clinic the morning of Day 0. The ABPM will be collected and the data contained therein will be downloaded and analyzed. A determination will be made based upon these ABPM data as to whether or not the subject meets the BP criteria for enrollment. No subject will be randomized until these baseline ABPM data have been reviewed and it has been documented that the subject meets entry BP criteria.

If the SBP_{day} is less than or equal to 135 mmHg, the subject will be deemed to be normotensive, from a clinical trial standpoint. The subject will not be enrolled in the study. The subject's primary care doctor will be informed that he/she has been found not to be hypertensive.

If the SBP_{day} is greater than 135 mmHg and ≤ 169 mmHg and the DBP_{day} ≤ 110 mmHg, the subject will be deemed to be hypertensive and to meet the BP criteria for this trial. These subjects will undergo additional baseline procedures as described below.

If the subject's BP is too elevated for them to continue safely in the study (i.e., SBP_{24h} > 169 mmHg and/or DBP_{24h} > 110 mmHg), the subject will be instructed to resume taking their prescribed BP medication as directed by the study doctor or general practitioner. The subject will not be enrolled in the study.

Subjects who meet the BP criteria for the trial following completion of the 10- to 14-day washout period will undergo the following additional baseline procedures:

1. Solicit history of PTAEs since prior visit;
2. Review and record medications taken since last visit;
3. Targeted physical examination (see Section 8.2);
4. Body weight while only wearing underwear and a light gown;
5. Vital signs (BP, pulse rate, respiration rate, and oral body temperature);
6. Orthostatic hypotension evaluation (see Section 8.4);
7. Blood sampling for serum chemistry (see Appendix B for list of tests);
8. Review of inclusion/exclusion criteria.

Subjects that continue to meet all eligibility requirements will be enrolled in the study and randomized 3:3:1 to one of three treatment arms. The subjects will then be administered their first dose of study drugs in the clinic.

TEAE monitoring will begin immediately following administration of the first dose of study drugs and will continue throughout the study. Any untoward medical occurrence that initiates or worsens after the first dose of study drugs and within 14 days of the last dose of study drugs will be recorded as a TEAE. Subjects will remain in the clinic under observation for one hour following their first dose and will be solicited for TEAE history prior to leaving the clinic. Prior to leaving the clinic, the following procedures will be performed:

1. Instruct subjects to continue to not take their prescribed BP medication;
2. Instruct subjects to continue to not take any NSAIDs, calcium channel blockers, or investigational drugs (other than the study drugs);
3. For WCBP: Instruct subjects to continue to use adequate contraceptive methods;

4. Provide subjects with sufficient study drugs for the remainder of the 2-week treatment period and instruct subjects to take the study drugs qd in the morning at home, except for the mornings of Days 6 and 13 when the drug will be taken in the clinic. The subjects will be instructed to take the Day 1-5 study drugs between 0700 and 1000 hours, and preferably at approximately the same time each day;
5. Provide subjects with a diary and instruct subjects to record any concomitant medications taken and details of study drug administration;
6. Instruct subjects to return to the clinic in 6 days (the morning of Day 6), and to bring the completed diary and study drug containers with any unused study drug.

6.3 Study Day 6

Subjects will return to clinic on the morning of Day 6 and will undergo the following procedures:

1. Solicit history of TEAEs since the previous visit;
2. Collect study drug containers and count and record unused study drug;
3. Review diary for details of study drug administration and any concomitant medications taken since the previous visit;
4. Provide subjects with ABPM, instruct in its use, and check the positioning of the ABPM.

Following the placement of the ABPM, the subjects will be administered their Day 6 dose of study drugs in the clinic. Prior to leaving the clinic, the following procedures will be performed:

1. Instruct subjects to wear the APBM at all times for the next 25 hours;
2. Subjects will be given back their remaining study drug supply and instructed to take the Day 7 study drugs at home 24 hours \pm 1 hour after the Day 6 study drugs;
3. Subjects will be given back their diary and instructed to record any concomitant medications taken and details of study drug administration;
4. Instruct subjects to return to the clinic the following day (on the morning of Day 7), and to bring the completed diary and study drug containers with any unused study drug.

6.4 Study Day 7

The Day 7 study drugs will be self-administered at home within 24 hours \pm 1 hour from the Day 6 dose. Subjects will return to clinic on the morning of Day 7 (after the home administration of study drugs). The following evaluations will be performed:

1. Solicit history of TEAEs since the previous visit;
2. Review diary for details of study drug administration and concomitant medications since the previous visit;

3. Collect study drug containers, and count and record unused study drug;
4. Targeted physical examination (see Section 8.2);
5. Body weight while only wearing underwear and a light gown;
6. Vital signs (BP, pulse rate, respiration rate, and oral body temperature);
7. Orthostatic hypotension evaluation (see Section 8.4);
8. Collect the ABPM and download the systolic and diastolic BP values obtained by the ABPM and incorporate into the subject's medical record and CRF;
9. Blood sampling for measurement of creatinine (and calculation of creatinine clearance) and electrolytes (sodium, bicarbonate, calcium, chloride, phosphorous, and potassium).

If, after completing the Day 7 evaluations, the Investigator determines that it is safe for the subject to continue in the study, the following procedures will be performed:

1. Instruct subjects to continue to not take their prescribed BP medication;
2. Instruct subjects to continue to not take any NSAIDs, calcium channel blockers, or investigational drugs (other than the study drugs);
3. For WCBP: Instruct subjects to continue to use adequate contraceptive methods;
4. Subjects will be provided back their remaining study drug supply and instructed to take qd in the morning at home starting with the morning dose on Day 8, except for the study drugs on Day 13 which are to be taken in clinic. The subjects will be instructed to take the Day 8-12 study drugs between 0700 and 1000 hours, and preferably at approximately the same time each day;
5. Subjects will be provided back their diary and instructed to record any concomitant medications taken and details of study drug administration;
6. Instruct subjects to return to the clinic in 6 days (on the morning of Day 13), and to bring the completed diary and study drug containers with any unused study drug.

If during the Day 7 visit, the subject's BP is too elevated for them to continue safely in the study (i.e., SBP_{24h} > 169 mmHg and/or DBP_{24h} > 110 mmHg), blood will be drawn for renal profile testing (see Section 8.5). The subject will be instructed to cease taking study drugs, instructed to resume taking their prescribed BP medication as directed by the study doctor or general practitioner, given back their diary and instructed to record any concomitant medications taken between visits, and instructed to return to the clinic in 7 days (Day 14).

6.5 Study Day 13

Subjects will return to clinic on the morning of Day 13 (except for those discontinued from study drug due to excessive hypertension or other safety reasons at Day 7) and will undergo the following procedures:

1. Solicit history of TEAEs since the previous visit;
2. Review diary for details of study drug administration and concomitant medications since the previous visit;
3. Collect study drug containers and count and record any unused study drug;
4. Provide subjects with an ABPM, instruct in its use, and check the positioning of the ABPM.

Following the placement of the ABPM, the subjects will be administered their Day 13 dose of study drugs (final dose) in the clinic. Prior to leaving the clinic, the following procedures will be performed:

1. Instruct subjects to wear the APBM at all times for the next 25 hours;
2. Subjects will be given back their diary and instructed to record any concomitant medications taken between visits;
3. Instruct subjects to return to clinic the following day (on the morning of Day 14), and to bring the completed diary to the clinic.

6.6 Study Day 14

Subjects will return to clinic on the morning of Day 14. The following evaluations will be performed:

1. Solicit history of TEAEs since the previous visit;
2. Review diary for details of concomitant medications since the previous visit;
3. Comprehensive physical examination (see Section 8.2);
4. Body weight while only wearing underwear and a light gown;
5. Vital signs (BP, pulse rate, respiration rate, and oral body temperature);
6. Collect the ABPM and download the systolic and diastolic BP values obtained by the ABPM and incorporate into the subject's medical record and CRF;
7. Orthostatic hypotension evaluation (see Section 8.4);
8. 12-lead ECG;

9. Blood sampling for hematology and serum chemistry (see Appendix B for list of tests);
10. Collection of urine for urinalysis (see Appendix B for list of tests);
11. Urine pregnancy test for WCBP only;
12. Blood sample will be collected at 24 hours \pm 1 hour post-dose for measurement of amlodipine concentrations. Only subjects enrolled at Investigational Sites that have UV-shielded lights will participate in the PK blood collections. Due to the design of the trial (randomized, double-blind, placebo-controlled), this blood sample will be collected and analyzed for all participating subjects, regardless of whether they are in a treatment arm that receives amlodipine.

Following the Day 14 evaluations, the following procedures will be performed:

1. Instruct subjects to resume taking their prescribed BP medication as directed by the study doctor or general practitioner;
2. Instruct subjects to continue to not take any NSAIDs or investigational drugs for the remainder of the study (through Day 28);
3. For WCBP: Instruct subjects to continue to use adequate contraceptive methods for the remainder of the study (through Day 28);
4. Subjects will be provided back their diary and instructed to record any concomitant medications taken between visits;
5. Subjects will be instructed to return to the clinic in 14 days (Day 28) for final study visit (follow-up visit), and to bring the completed diary to the visit.

6.7 Study Day 28

Subjects will return to clinic on Day 28 for their final study visit (follow-up visit). The following evaluations will be performed:

1. Solicit history of TEAEs since last visit;
2. Review diary for details of concomitant medications taken since last visit;
3. Targeted physical examination (see Section 8.2);
4. Vital signs (BP, pulse rate, respiration rate, and oral body temperature).

For subjects whose study drug is discontinued at Day 7, this follow up-visit will still occur on Day 28 (i.e., these subjects will return to the clinic for both the Day 14 and Day 28 visits).

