

Study Day 0: When the subjects return to clinic the following day, the ABPM will be collected and the data contained therein downloaded and analysed. If subjects are found to be hypertensive, based upon their ABPM measurement, they will undergo additional baseline procedures as described below. If the subject's BP is too elevated for them to continue safely in the study (i.e., SBP_{24h} > 169 mmHg or DBP_{24h} > 110 mmHg), the subject will not be enrolled and they will be instructed to resume taking their prescribed BP medication as directed by the study doctor or general practitioner. If the subject is found to be normotensive (SBP_{day} ≤ 135 mmHg), the subject will not be enrolled. The subject's primary care doctor will be informed that he/she has been found not to be hypertensive. No subject will be randomized until these baseline ABPM data have been reviewed and it has been documented that the subject meets entry BP criteria.
 
Subjects who meet the BP criteria (SBP_{day} > 135 and ≤ 169 mmHg and DBP_{day} ≤ 110 mmHg) following completion of the 10- to 14-day washout period will undergo the following additional baseline procedures: solicit for history of PTAEs since the previous visit, targeted physical examination, body weight in underwear and a light gown, vital signs, orthostatic hypotension evaluation, serum chemistry, and record medications taken since last visit. Subjects that continue to meet all eligibility requirements will be enrolled in the study and randomized 3:3:1 to one of three treatment arms. The subjects will then be administered their first dose of study drugs in the clinic.
 
Monitoring for treatment emergent adverse events (TEAEs) will begin immediately following administration of the first dose of study drugs and will continue throughout the study. Any untoward medical occurrence that initiates or worsens after the first dose of study drugs and within 14 days of the last dose of study drugs will be recorded as a TEAE. Subjects will remain in the clinic under observation for one hour following their first dose and will be solicited for TEAE history prior to leaving the clinic. Subjects will be provided with sufficient study drugs for the remainder of the 2-week treatment period, and instructed to take the study drugs qd in the morning. Subjects will be provided with a diary and instructed to record any concomitant medications taken and details of study drug administration. Subjects will be instructed to return to clinic the morning of Day 6.
 
Study Day 6: Subjects will return to clinic on the morning of Day 6 and will be solicited for history of TEAEs since the previous visit. The study drug containers will be collected and unused study drug counted and recorded. The diary will be reviewed for details of study drug administration and any concomitant medications taken since the previous visit. Subjects will be given an ABPM, instructed in its use, and have the positioning of their ABPM checked. The subjects will then be administered their Day 6 dose of study drugs, and instructed to wear the ABPM at all times for the next 25 hours. Subjects will be given back their remaining study drug supply and diary, instructed to record any concomitant medications taken and details of study drug administration, and instructed to return to clinic the following day.
 
Study Day 7: The Day 7 study drugs will be self-administered at home within 24 hours ± 1 hour from the Day 6 dose. Subjects will return to clinic on the morning of Day 7 (after the home administration of study drugs). The diary will be reviewed for any concomitant medications taken and for details of study drug administration since the previous visit. The study drug containers will be collected and unused study drug counted and recorded. Subjects will be solicited for history of TEAEs since the previous visit. A targeted physical examination will be performed and body weight in underwear and light gown and vital signs will be measured. An orthostatic hypotension test will be performed. Subjects will have BP as measured by the ABPM recorded and the ABPM collected. Subjects will have blood collected for measurement of creatinine (and calculation of creatinine clearance) and electrolytes.
 
If the Investigator determines that it is safe for the subject to continue in the study, the subject will have their remaining study drug supply returned to them, and instructed to take the study drugs at home on Days 8-12, between 0700 and 1000 hours, and preferably at

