4. ELIGIBILITY CRITERIA

4.1 Inclusion Criteria

A subject may be included in this study if he or she meets all of the following criteria:

1. Adult 40 to 75 years of age;
2. Existing hypertension that is being treated using pharmacological therapy with a single agent that is not a calcium channel blocker;
3. $SBP_{day} > 135$ and ≤ 169 mmHg and $DBP_{day} \leq 110$ mmHg at Day 0 (i.e., after the 10- to 14-day washout from prior BP medication);
4. Body Mass Index (BMI) of 18.5 to 34.9 kg/m²;
5. Healthy (other than hypertension) as determined by the Investigator based on medical history, physical examination, vital signs, 12-lead ECG, and clinical laboratory tests;
6. A negative pregnancy test at initial screening visit;
7. If WCBP, agree to use a highly effective form of birth control while on study (from Screening through final study visit);

Highly effective methods of birth control are defined as those, alone or in combination, that result in a low failure rate (i.e., less than 1% per year) when used consistently and correctly. Forms of birth control include intrauterine device (IUD), birth control patch or vaginal ring, oral, or injectable or implanted contraceptives, or a vasectomized partner, or abstinence from sexual intercourse. Abstinence is acceptable only as true abstinence: when this is in line with the preferred and usual lifestyle of the subject. Periodic abstinence (e.g., calendar, ovulation, symptothermal, post-ovulation methods) and withdrawal are not acceptable methods of contraception.

A woman that is postmenopausal (≥ 2 years since last menstrual period) or permanently sterilized (e.g. tubal occlusion, hysterectomy, bilateral salpingectomy) is not considered a WCBP.

8. Able to comprehend and sign an ICF.

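### Day 0 disposition rules clear treated hypertensives on systolic pressure alone, and give no resume instruction to some subjects above the daytime entry limits

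*Protocol*

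**What the plan says.** **Who reaches Day 0.** Inclusion criterion 2 (Protocol 4.1) requires "Existing hypertension that is being treated using pharmacological therapy with a single agent". Protocol 6.1.1 then instructs these subjects: "Cease taking current BP medication". That instruction has no end date, although the NSAID, calcium channel blocker and investigational-drug restrictions listed with it do. Protocol 5.6 says the current BP drug is not to be taken between the initial screening visit and Day 14.

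**The three Day 0 branches in Protocol 6.2.**
1. SBPday of 135 mmHg or less: "the subject will be deemed to be normotensive, from a clinical trial standpoint". The subject is not enrolled, and the "primary care doctor will be informed that he/she has been found not to be hypertensive".
2. SBPday "greater than 135 mmHg and ≤ 169 mmHg and the DBP_{day} ≤ 110 mmHg, the subject will be deemed to be hypertensive", and the subject goes on to baseline procedures.
3. A pressure described as "too elevated for them to continue safely in the study (i.e., SBP_{24h} > 169 mmHg and/or DBP_{24h} > 110 mmHg"). Enrolment is refused, and this branch alone deals with the stopped drug, in these words: "the subject will be instructed to resume taking their prescribed BP medication as directed by the study doctor or general practitioner".

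The synopsis and Protocol Section 3 carry the same rules. There the message reads "primary care doctor will be informed that he/she has been found not to be hypertensive. No subject will be randomized", and the limiting phrase about the trial's standpoint is absent altogether. SAP Section 3 repeats the message and both sets of limits in the past tense.

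**The concern.** Both faults affect people who fail screening after the trial has taken them off treatment.

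**Message.** Branch 1 sends a diagnosis out of the trial to the doctor who will decide about restarting treatment. Section 6.2 limits its own label to the trial's purposes, but the report to the doctor carries no such limit. Nothing requires the report to mention the readings or that the trial stopped the drug. The trigger is systolic only, although the labelling in Appendix F (section 12.2) describes diastolic 90 to 104 mmHg as mild hypertension.

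**Gap.** Branch 2 uses daytime means and branch 3 uses 24-hour means, with the same numbers, 169 and 110. Daytime pressure usually exceeds the 24-hour mean, so the two limits do not meet. A subject between them is too high to enter but does not trigger the only Day 0 instruction to go back on treatment. Meanwhile the standing text (5.6 and 6.1.1) points towards staying off it.

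**Working it through.** The plan states no figure to reproduce. The check is to apply the three rules of Protocol 6.2 as written.

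**Rules (mmHg).**
- Message: SBPday ≤ 135.
- Enrol: 135 < SBPday ≤ 169 and DBPday ≤ 110.
- Too elevated: SBP24h > 169 or DBP24h > 110.

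**Test cases.** The values are chosen for the check and are not from the documents.

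| SBPday/DBPday | SBP24h/DBP24h | Branches that apply |
|---|---|---|
| 150/95 | 145/90 | enrol |
| 134/95 | 128/90 | message |
| 134/113 | 128/108 | message only, although DBPday exceeds 110 |
| 134/116 | 130/112 | message and too elevated |
| 172/100 | 165/95 | none |
| 160/113 | 150/107 | none |
| 170/111 | 168/108 | none |

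**General result.** With SBP24h ≤ 169 and DBP24h ≤ 110 the too-elevated branch is off. With SBPday > 135 the message branch is off. The enrol branch is then off if SBPday > 169 or DBPday > 110. So the uncovered group is SBPday > 169, or SBPday > 135 with DBPday > 110, with both 24-hour means within limits. A subject with SBPday ≤ 135 and DBPday > 110 is covered, but by the message.

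**Other places that might close the gap.**
- Protocol 4.3 item 3 uses the same 24-hour limits. Items 4 and 10 rest on the investigator's judgement and carry no resume instruction.
- The resume text in 5.6 concerns Day 7 and Day 14; that in 6.6 concerns Day 14.
- The reminder in 6.2 to keep off the usual drug is given only after enrolment.

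**Width of the gap, for illustration only.** Daytime (09:00 to 21:00) is 12 of the 24 analysed hours. Let D be the daytime mean minus the mean of the other 12 hours. With no missing readings:

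SBP24h = (12 × SBPday + 12 × (SBPday − D)) / 24 = SBPday − D/2

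For SBPday 172 and assumed D of 10, 15 or 20, SBP24h is 167, 164.5 or 162. All are at or below 169, so no branch applies. The uncovered systolic range runs from above 169 up to 169 + D/2, which is 174, 176.5 or 179. The documents give no value for D.

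**The case against.** The other side has several fair points.

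- **The recording is substantial.** A reader might infer that the message rests on a single systolic reading. It does not. SBPday is a time-weighted daytime mean, the white-coat window is excluded, and Protocol 10.7 requires at least 21 daytime readings (20 within tolerance). This stands: the weakness is one off-drug session and no diastolic term.
- **Care is handed back.** The message goes to the subject's own doctor, and the protocol does not forbid sending the values. That is true for the first group only, and what is required is a conclusion rather than the readings.
- **Eligibility is secure.** A reader might infer that subjects in the gap could be randomised. Inclusion criterion 3, and the rule that entry BP must be documented before randomisation, prevent that. The gap is in disposition only.
- **Some handling exists.** Protocol 8.1.4 lists hypertension among expected pretreatment events, so a rise during washout can be recorded with the action taken (8.1.6). This is weaker than the written instruction given to too-elevated subjects.
- **Few may be affected.** Exclusion criterion 1 already removes resting pressure above 169/110 on therapy.

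A reader might also try to estimate how many subjects given the message would exceed 135 on a repeat recording, using the prior study's placebo-arm SD of 8.2 mmHg for change (Appendix H). The documents do not support that. It ignores regression to the mean in people selected for a low value, and that study enrolled newly diagnosed subjects.

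**Conclusion.** Both faults stand on the text of Protocol 6.2, the synopsis, Protocol Section 3 and SAP Section 3. The first is an unqualified, systolic-only message about known treated hypertensives, which can also conflict with the too-elevated branch. The second is a mismatch between daytime and 24-hour limits that leaves some ineligible subjects without the resume instruction.

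The size is minor. The documents give no screen-failure rate or baseline distribution, so the number affected is unknown, and any band width depends on an assumed D. Only Day 0 screen failures are concerned; sample size, alpha and the analysis of randomised subjects are untouched.

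Two opposite readings of the medication text go too far. One is that these subjects are simply not addressed: 5.6 bars the drug from the initial screening visit to Day 14, and 6.1.1 sets no end to the stop. The other is that the protocol deliberately keeps screen failures off treatment: no text says so. What is missing is a release at Day 0.

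The consent form is not among the documents, so the conclusion covers the protocol and SAP text only.

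**What to change.** In Protocol 6.2, the synopsis and Protocol Section 3:

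(a) Replace the message in the SBPday ≤ 135 branch. State that the subject, off drug, did not meet the trial's entry BP limit; give SBPday, DBPday, SBP24h, DBP24h and the days off drug; and ask the doctor to review BP treatment.

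(b) Add SBPday > 169 or DBPday > 110 to the too-elevated branch, so that its resume instruction applies, and state that this branch takes precedence over the SBPday ≤ 135 branch.

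(c) Align the Day 0 description in SAP Section 3.

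Under (b), 172/100, 160/113, 170/111, 134/113 and 134/116 in the table all go to the too-elevated branch alone. The 134/95 case gets the revised message and 150/95 is enrolled as before. Every subject then has a disposition.

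The cost is two sentences in three places in the protocol plus the matching SAP text. The ABPM data are already downloaded and analysed on Day 0, so no visit, procedure or analysis is added.
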